Human Research Protocol

Title: Randomized Trial of Text vs. Video Patient Educational Materials in Cirrhosis

PI: [name] MD

Version 0.5

Version Date: 10/7/2021

Background and Significance

Cirrhosis is a complex chronic disease, with several associated complications, numerous symptoms, and patients often require many medications. Cirrhosis is unfortunately linked to frequent hospitalizations and re-hospitalizations. Lack of medication compliance leads to hospitalizations, and increased disease understanding can improve medication compliance. Improved health literacy can prevent hospitalizations in other ways (preventing ED visits for ascites or HE). Based on internal QI data, we know that many patients with cirrhosis at U-M do not understand their medications and other aspects of their disease. Our essential purpose in this study is to compare the efficacy and patient satisfaction associated with traditional text cirrhosis education vs. recently-created educational videos on the same topics.

Specific Aims:

Aim 1: *Do educational materials improve patients' understanding of disease?*

Assess change in score for pre- and post-evaluations.

Aim 2: *Is one mode of patient education more effective than the other?*

Compare efficacy of educational materials when presented as text (Cirrhosis Toolkit) or video.

Aim 3: *Do patients prefer one mode of education over the other?*

Compare patients' preference for educational materials presented as text (Cirrhosis Toolkit) or video.

Aim 4: *How can these educational materials be improved?*

Collect feedback from patients on educational materials.

Research Design and Methods

Overview

We plan to enroll adult outpatients with cirrhosis who are evaluated at the University of Michigan Hepatology Clinic. We aim to enroll a maximum of 320 subjects with cirrhosis, into two main study arms. Arm 1 will include 160 responses from subjects who are newly diagnosed with cirrhosis, and Arm 2 will include 160 responses from subjects with history of cirrhosis.

After screening, and before being invited to respond to the study survey, participants will be randomized into one of 4 subgroups per each study arm, for a total of 8 possible subgroup assignments:

Arm 1: New Diagnosis		Arm 2: Previous Diagnosis	
1A: Cirrhosis Toolkit	1B: Cirrhosis Videos	2A: Cirrhosis Toolkit	2B: Cirrhosis Video
1A.1: General Cirrhosis Info	1B.3: General Cirrhosis Info	2A.1: General Cirrhosis Info	2B.3: General Cirrhosis Info
1A.2: Ascites Info	1B.4: Ascites Info	2A.2: Ascites Info	2B.4: Ascites Info

Subgroups 1 and 2 will involve the presentation of educational materials in text-and-graphic format (Cirrhosis Toolkit), with each subgroup focusing on a single subject or section of the material. Subgroups 3 and 4 will be presented with similar material in video format, also focusing on a single subject per subgroup. Recruitment for this study will conclude once 40 subject-experiments have been completed for each subgroup.

Subjects will be given the option to be randomized into an additional study subgroup (For example: if they were randomized into subgroup 1A.1 in the first round, they would be randomized into 1A.2 or 1B.4 for their second round of participation) and participate in the study a second time. Enrollment will conclude once 160 subject-experiments have been completed for each study arm.

Inclusion Criteria

1. Age 18 years or older
2. Cirrhosis, as diagnosed by imaging, elastography, biopsy, or decompensation
3. Available email address
4. Arm 1: New patient visit for cirrhosis (and diagnosis within the last 6 months)
5. Arm 2: Previous cirrhosis diagnosis (>6 months)

Screening

For Arm 1, patients with a new diagnosis of cirrhosis will be identified by reviewing the University of Michigan Hepatology Clinic outpatient schedule and related notes in the Electronic Medical Record.

For Arm 2, Patients with >6 months history of cirrhosis diagnosis will be identified via Datadirect, previously established patient lists, and the University of Michigan Hepatology Clinic outpatient schedule.

Patients who meet the inclusion criteria will be randomized into one of the above subgroups and sent an email invitation to participate in the study. Potential participants will not be called or approached in person. The study invitation message will include contact information for study staff members in case these patients have any questions or would like to discuss the study in more detail before proceeding.

Procedures

The study will be conducted completely online, via REDCap. The initial study invitation email will include a link to the REDCap database, where participants will complete study questionnaires and activities. Informed consent for this study will be conducted online via REDCap.

Demographics Survey

Participants will be asked to report their age, sex, cause of cirrhosis, and any history of ascites, variceal bleeding, or HE.

Pre-Evaluation

Based on their randomly assigned subgroup, participants will complete a Pre-Evaluation, consisting of 5-6 content-specific questions, to determine each participants' baseline level of content knowledge. Pre-Evaluation scores will be recorded, but not presented to participants.

Educational Intervention

Participants will be prompted to review the educational material associated with their assigned subgroup. This will involve reading a specific section of the Cirrhosis Toolkit or watching videos. Participants will be given unlimited time to review and interact with educational materials and will be prompted to complete the Post-Evaluation when ready.

Post-Evaluation

Participants will be directed to respond to a set of content-specific questions identical to the Pre-Evaluation they completed earlier in the study, but in a randomized order. Post-Evaluation scores will be presented to participants after they complete the optional feedback survey (below).

The change in score between pre-and-post-evaluations for each participant will inform the results of aims 1 and 2. For questions with multiple correct answers, no partial credit will be awarded.

Debrief

Participants will be informed that all mandatory study activity has been completed and thanked for their time.

The study debrief will present participants with multiple optional study activities:

- 1) Complete the Feedback Survey
- 2) Contact study staff for further questions
- 3) Review their Post-Evaluation Score and complete a brief survey response
- 4) Re-enroll in the study to 'learn more'

- 1) The Feedback Survey will consist of questions related to aims 3 and 4.

Questions:

- Did you find this material helpful? (Likert scale)
- Would you recommend this material to others? (yes/no)
- Would you prefer further educational materials in text or video format?
- Do you have any suggestions for improving these educational materials? (text box)

- 2) Participants will be given contact information for study staff members if they have any further questions.

3) Participants will have the option to review their post-evaluation scores only after all other activities have been completed, such as the feedback survey. Scores will be reported as [# correct]/[# of questions] Participants will be asked to reflect on their score:

-Are you satisfied with your score? (visual analog scale or Likert)

-What are your next steps for further education? (select all that apply: Nothing, talk to Hepatologist, talk to Nurse, talk to nutritionist, talk to other medical professional, internet search, talk to family and friends, other (please explain))

4) Participants will be given the option to 'learn more' and re-enroll in the study. If participants elect to re-enroll, they will be randomized into a different subgroup of the same study arm.

Statistical Analysis

Aim 1: Matched pair Wilcoxon comparing pre-test and post-test scores in the whole study population.

Aim 2: Matched pair Wilcoxon comparing score change (from pre to post) between video group and text group.

Aim 3: Descriptive statistics of Likert scale results.

Aim 4: Will report key themes from patient open-ended responses.

Foreseeable Risks and Discomforts

The risks of this study are primarily psychological. Subjects may become frustrated if performing poorly on the pre-or-post-evaluations. Patients may have privacy concerns about study communication via email or conducting study activities online or on their personal device.

Expected Benefits

A potential direct benefit for participants is the opportunity to learn something new about cirrhosis.

Privacy and Confidentiality

Redcap, a secure and HIPAA-compliant electronic program, will be used for all data collection and study activities. Once randomized, participants will be identified only by a study ID number. Results of the testing and any other information provided by the subject are available for analysis under the heading of this number only, not by name or other personally identifiable information. No names or personally identifiable information will be collected or used in any publications.

We will keep a separate password protected screening log on the University shared drive in a secured location. Only study personnel will have access to the electronic screening log that maps the Subject ID number and Screening ID number (if applicable) to the participant's email address. Only limited identifiable data will be collected for screening purposes.

Data and Safety Monitoring

There are no safety concerns in this study. We will store data on a secure U-M server. Study staff will proofread data weekly to verify accuracy. PI will complete a comprehensive review of all data prior to analysis.

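### The Aim 2 text-video comparison leaves out diagnosis arm and topic, the factors the design is built on; this does not bias it, but may cost power

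*Combined protocol and SAP*

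**What the plan says.** The Overview describes two diagnosis arms. The first is defined by "Arm 1 will include 160 responses from subjects who are newly diagnosed with cirrhosis" and the second by "Arm 2 will include 160 responses from subjects with history of cirrhosis". Within these, "participants will be randomized into one of 4 subgroups per each study arm, for a total of 8 possible subgroup assignments": two formats (text toolkit or video) crossed with two topics (general cirrhosis or ascites). Two stopping statements follow: "Recruitment for this study will conclude once 40 subject-experiments have been completed for each subgroup" and "Enrollment will conclude once 160 subject-experiments have been completed for each study arm".

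The quotas count responses. A participant may be randomised a second time within the same arm, and that second round counts. The ceiling, by contrast, is worded in people: "We aim to enroll a maximum of 320 subjects with cirrhosis, into two main study arms".

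Under Pre-Evaluation, the test has 5-6 questions specific to the assigned content, and the Post-Evaluation repeats them. Under Statistical Analysis, Aim 1 is a paired comparison over the whole study population. Aim 2 reads in full: "Matched pair Wilcoxon comparing score change (from pre to post) between video group and text group". No stratification, covariate, per-arm estimate or interaction is named. That Aim 2 pools over arm and topic is inferred from this silence; for Aim 1 the pooling is explicit.

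**The concern.** Arm and topic are part of the design. Arm has its own eligibility criterion, screening sources and quota, and topic is a randomised factor with its own test. Newly diagnosed patients may know less at the start and gain more. One topic may also be easier to learn, or scored on a different number of items. If one test has five items and the other six, a single extra correct answer is worth 20% on one and 16.7% on the other.

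An analysis that ignores these factors treats such differences as noise in the text-video comparison. What is at stake is the power of Aim 2, not the validity of its overall result.

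**Working it through.** **Design counts.** The plan gives no power calculation, so only the counts can be reproduced: 4 × 40 = 160 per arm and 8 × 40 = 2 × 160 = 320. They agree. Text against video is then 160 v 160 overall and 80 v 80 within an arm.

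**Assumptions (none is in the documents).** Two-sided 5% level; independent responses; an unpaired comparison; within-cell SD of score change set to 1; a format effect of 0.315 SD, chosen so that the stratified analysis has 80% power. Let a be the gap in mean change between arms and t the gap between topics, both in within-cell SD.

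**Variance left in the error term.** In balanced cells, each two-level factor adds the square of half its gap:

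ratio = 1 + (a/2)² + (t/2)²

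**Power.** The standard error is √(2/160) = √(1/80) within strata, and is multiplied by √ratio when pooled:

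power = Φ(0.315 × √80 / √ratio − 1.96)

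Stratified: 0.315 × 8.944 − 1.96 = 0.86, so 80%. The last column is 320 × (1 − 1/ratio).

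| Arm gap, topic gap (SD) | Ratio | SE increase | Pooled power | Equivalent responses lost of 320 |
|---|---|---|---|---|
| 0, 0 | 1.000 | 0% | 80% | 0 |
| 0.3, 0.3 | 1.045 | 2% | 79% | 14 |
| 0.5, 0.5 | 1.125 | 6% | 76% | 36 |
| 0.5, 0.8 | 1.2225 | 11% | 72% | 58 |
| 1, 1 | 1.500 | 22% | 63% | 107 |

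**Check with rank tests.** Rounded scores were simulated with 40 per cell and 4,000 runs per setting. At a format effect of 0.33 SD, the unstratified rank-sum test against the van Elteren test had power of 77% v 80% with both gaps 0.5 SD, and 65% v 80% with both 1 SD. With no gaps both were at about 80%. With no format effect, the unstratified test rejected in 4.5% of runs without gaps and about 1.5% with both gaps 1 SD. It is therefore conservative.

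**Precision by arm.** The 95% half-width for format within one arm is 1.96 × √(2/80) = 0.31 SD. For the arm-by-format contrast it is 1.96 × √(4/80) = 0.44 SD.

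**Effect of second rounds.** If everyone took part twice, each arm would hold 160/2 = 80 people. Using first rounds only, split evenly by format, the half-widths become 1.96 × √(2/40) = 0.44 SD and 1.96 × √(4/40) = 0.62 SD.

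**The case against.** The strongest reply is that the loss is hypothetical. The documents supply no SD, effect or gap. With equal mean change across arms and topics nothing is lost, and gaps of 0.5 SD cost about four points of power. That stands: the case rests on the fix being nearly free, not on a demonstrated large loss.

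Some stronger readings are tempting and should be resisted.

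- *Pooling biases Aim 2.* It does not. Format is randomised within arm and the cells are planned to be equal, so the arm and topic mix is the same for text and video.
- *The pooled result is an artificial half-and-half mix of arms.* A test stratified over four equal strata gives the arms the same weights, and the documents report no clinic case mix to compare with.
- *Aim 1 loses precision too.* No such loss has been shown. Aim 1 asks one overall question, expressly in the whole population.
- *The plan wrongly hides an effect confined to one arm.* No aim asks about arms. An effect of 0.4 SD in one arm and none in the other would average to 0.2 SD, but that 0.4 SD contrast lies inside the ±0.44 SD half-width. An arm-by-format test reaches 80% power only at about 2.80 × √(4/80) = 0.63 SD. Per-arm figures are informative but could not settle the matter.
- *The quotas are 160 patients per arm.* They are responses. This weakens every figure that assumes independence, and a van Elteren test on all responses would share the problem.

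It is also fair to say that the matched-pair form of the Aim 2 test is the more basic difficulty. Most text-video comparisons are between different people. Only a repeater who switches format supplies a within-person pair, and under the Overview's example that pair would span two topics.

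**Conclusion.** The point holds as a modest, specific improvement to Aim 2. The analysis omits two factors that the design controls. The consequence is a conservative test with an unknown loss of power: nil without gaps, about 1 to 4 points for gaps of 0.3 to 0.5 SD in both factors, and about 17 points if both gaps are 1 SD. These figures assume balanced cells, independent responses and an unpaired test. Repeat participation would reduce the information below what they imply. The documents do not support a finding of bias, of inflated false positives, or of a failure to answer any stated aim.

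**What to change.** Replace the Aim 2 sentence with one of these:

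- **Preferred:** a model of score change (or post score adjusted for pre score), on a percent-correct scale, with terms for format, arm and topic, and a participant random effect or cluster-robust standard errors for repeaters.
- **Alternative:** a van Elteren test stratified by the four arm-by-topic strata, using first-round responses only. This avoids the independence problem but discards second rounds. If everyone repeated, leaving 80 v 80 people, power at 0.315 SD would be Φ(0.315 × √40 − 1.96), about 51%.

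Keep Aim 1 as an overall result. Add a small table of the Aim 1 change and the Aim 2 format difference by arm with 95% confidence intervals, labelled descriptive. Expect half-widths of about ±0.31 SD per arm and ±0.44 SD for the arm-by-format contrast, and wider ones if second rounds mean fewer distinct people.

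The cost is a short paragraph and one table, with no extra patients or questions. Both rounds must be linked to the same person, so confirm that re-enrolment keeps the study ID or can be traced through the screening log. The second-round rule should also be reconciled: the Overview's example allows only the other topic, while the Debrief section allows any different subgroup of the same arm.

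### Aim 2 can use only completed experiments; if both stopping rules are met every cell ends at 40, so final counts would not show loss by format, and the plan has no analysis that allows for such loss

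*Combined protocol and SAP*

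**What the plan says.** **Timing of assignment.** The Overview puts randomisation ahead of contact: "After screening, and before being invited to respond to the study survey, participants will be randomized". Screening repeats the order: "Patients who meet the inclusion criteria will be randomized into one of the above subgroups and sent an email invitation". The subgroup fixes topic and format together. Online consent, demographics, Pre-Evaluation, material and Post-Evaluation follow (Procedures). Second-round assignment comes after the participant chooses to re-enrol (Debrief).

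**Stopping.** The Overview gives two rules, both counted in completed experiments: "Recruitment for this study will conclude once 40 subject-experiments have been completed for each subgroup", and "Enrollment will conclude once 160 subject-experiments have been completed for each study arm".

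**Outcome and analysis.** The Post-Evaluation section makes the pre-to-post change the outcome for Aims 1 and 2. The Statistical Analysis section gives Aim 2 one sentence, a Wilcoxon comparison of score change between video and text. It states no analysis set, no rule for experiments without a Post-Evaluation, and no reporting of numbers assigned or lost by format.

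**What is kept.** "Pre-Evaluation scores will be recorded, but not presented to participants", so a baseline exists for anyone who stops after that step.

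**The concern.** A change score does not exist without a Post-Evaluation. With no rule for incomplete experiments, the plan as written leads to a completers-only comparison. That is harmless if loss has nothing to do with format, or nothing to do with how much people would have learned. It is not harmless if both links are present, because the completers in the two formats are then no longer comparable groups.

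Unequal final group sizes are usually the first sign of such a problem. Here, meeting both stopping rules makes the final sizes equal by construction. Comparing text with video is part of the study's stated essential purpose, so a difference produced by who stayed, and not by what they learned, would affect a main conclusion. The direction cannot be predicted: the format that loses more people looks better if its leavers would have gained less, and worse if they would have gained more.

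**Working it through.** **1. The plan's own counts.** There are 4 subgroups per arm and 8 in all. 4 x 40 = 160 per arm and 8 x 40 = 320 in total, which agree with the stated figures. Each format occupies 4 cells, so 160 text and 160 video. Since 4 x 40 = 160, the subgroup rule and the arm rule are met together only at exactly 40 per cell.

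**2. What equal counts conceal.** The documents give no completion rate; 80% text and 60% video are assumed for illustration.
- Starts needed: 160/0.8 = 200 text and 160/0.6 = 267 video. The completed counts still read 160 and 160.
- If cells close at 40 under 1:1 assignment, text closes after about 200 starts, and the last 267 - 200 = 67 starts all go to video without randomisation of format.
- If instead only the 160-per-arm rule acted and no cell closed, each arm would end with about 160 x 0.8/1.4 = 91 text and 160 x 0.6/1.4 = 69 video, and the loss would show.

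**3. Possible bias.** Assumptions: independent experiments, 160 v 160 completers, no true format effect, and the SD of change unaffected by selection. r is the correlation between score change and the tendency to complete (treated as normal), equal in both formats unless stated.
- Bias in SD units = r x (L(p_low) - L(p_high)), where L(p) = phi(z_p)/p. L(0.8) = 0.350, L(0.7) = 0.497, L(0.6) = 0.644.
- Type I error = P(|Z + bias/sqrt(2/160)| > 1.96).
- Worked case, 80% v 60%, r = 0.3: bias = 0.3 x 0.294 = 0.088 SD; 0.088/0.112 = 0.79; type I error 12.4%.

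| Completion | r | Bias (SD) | Type I error, formula | Simulated rank-sum |
|---|---|---|---|---|
| 80 v 80 | any, equal | 0 | 5.0% | 4.4-5.8% |
| 80 v 70 | 0.1 | 0.015 | 5.2% | 5.3% |
| 80 v 70 | 0.3 | 0.044 | 6.8% | 6.3% |
| 80 v 70 | 0.5 | 0.073 | 10.1% | 10.8% |
| 80 v 60 | 0.1 | 0.029 | 5.8% | 6.4% |
| 80 v 60 | 0.3 | 0.088 | 12.4% | 12.1% |
| 80 v 60 | 0.5 | 0.147 | 26.0% | 27.0% |
| 80 v 60 | -0.3 | -0.088 | 12.4% | 12.0% |

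The simulation used 4,000 runs with integer changes (normal, mean 1, SD 1.5, rounded and limited to -6 to 6; all assumed).

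Equal completion is not proof of safety. With r = 0.3 in one format and -0.3 in the other, at 80% v 80%, the bias is 0.6 x 0.350 = 0.21 SD.

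**4. Which loss late assignment reaches.** A separate simulation (3,000 runs) took an SD of gain of 1.5 questions and, for video only, log-odds of continuing that rise by 0.5 per SD of gain. Bias in questions, format assigned before invitation and then after the Pre-Evaluation:
- format-related loss only before the Pre-Evaluation: 0.43, then 0.00
- only at the material: 0.22, then 0.22
- at both stages: 0.61, then 0.22

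The sizes follow from the assumptions. What carries over is that late assignment removes the first kind of loss and leaves the second untouched.

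**5. What a sensitivity analysis would show.** Let completers gain 1.0 item in both formats (assumed), with non-completers changing by gT (text) and gV (video). At 80% v 60%, text minus video = (0.8 + 0.2gT) - (0.6 + 0.4gV). Common values of -1, 0, 1 and 2 give +0.4, +0.2, 0 and -0.2 items. Letting the values differ by format gives -0.8 (gT = -1, gV = 2) to +1.0 (gT = 2, gV = -1).

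**The case against.** The strongest reply is that assigning format after the Pre-Evaluation does not mend what the counts conceal. Completed numbers are unchanged, and loss at the self-paced material, which is possible in any case, is untouched (step 4). That stands, so late assignment is offered only as a precaution.

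A reader might infer that patients know their format when they decide whether to take part. The documents do not support this. Patients are given a contact in case they "have any questions or would like to discuss the study in more detail before proceeding", but the invitation and consent texts are not in the file, and identical invitations may already be in use. Nor does early randomisation by itself bias Aim 2: loss must also depend on format and be related to score change.

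A reader might also take it that each cell closes at 40. No section says so. Equal counts follow only if both rules are met. If enrolment stopped on the arm total alone, unequal cells could reveal loss.

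Two practical objections stand and shape the fix. The Overview example has a participant who began in 1A.1 change topic ("they would be randomized into 1A.2 or 1B.4 for their second round of participation"), but the Debrief allows any different subgroup of the same arm, including 1A.1 to 1B.3. If the topic repeats, format is forced. Late assignment also needs one question set per topic for both formats, which is not stated.

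It is fair, too, that no final report is described, so silence on participant flow is not a refusal to report it. But flow counts alone would not change what Aim 2 concludes. Finally, a reader might infer from "We aim to enroll a maximum of 320 subjects with cirrhosis, into two main study arms" that the targets cannot be reached once people drop out. The same paragraph counts 160 responses per arm, so 320 can be read as 2 x 160 responses, and no shortfall is claimed.

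**Conclusion.** The point holds in a limited form. What follows from the text is that Aim 2 can use only experiments with a Post-Evaluation, that first-round format is randomised before invitation and consent, and that meeting both stopping rules gives 40 in every cell, so the final counts would not show loss by format. Whether bias results is not known. It needs loss that depends on format, in how many leave or in who leaves, and that is related to score change. Under the assumptions above the effect is minor at 80% v 70% with r up to 0.3 (type I error at most 6.8%). It becomes material only when both quantities are sizeable (26.0% at 80% v 60% with r = 0.5) or when r differs between formats. No completion rate, SD or correlation is given, so these figures show what could happen and do not predict it. The change is worth making because it is cheap and bears on a main comparison; confidence is medium.

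**What to change.** 1. **Assign topic first, format later.** Randomise text or video in REDCap only once the Pre-Evaluation is submitted, in both rounds, with the same questions for both formats of a topic. In round two use the other topic, as in the Overview example, and reconcile the Debrief wording with it. This removes any format-dependent loss before the material and gives every assigned experiment a baseline score.
2. **Define the Aim 2 set as every experiment so assigned.** Keep the main test on those with a Post-Evaluation. Add a sensitivity analysis that varies the assumed change of non-completers separately by format (negative, zero, equal to completers, larger than completers) and reports where the conclusion changes. No single value should be called a bound. Support it with assigned and completed numbers, and Pre-Evaluation scores of completers and non-completers, by format and round.
3. **Keep format randomised until enrolment stops**, so that no run of late starts goes to one format. Some cells may then pass 40, and the plan should say which of the two rules ends enrolment. If every cell must reach 40, cells of the better-completed format would end near 40/0.7 x 0.8 = 46 at 80% v 70%, or 40/0.6 x 0.8 = 53 at 80% v 60%. If the arm total of 160 governs, 80% v 60% gives about 91/2 = 46 and 69/2 = 34 per cell.

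**Cost.** A REDCap set-up change (assumed small; the documents give no effort figure), a few counts and baseline summaries, and one extra analysis whose range will be wide and should not replace the main test. Some cells may finish above 40: only a few experiments over when the completion gap is small, more when it is large. No completed experiment is lost.

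### One person can supply two of the 320 records, but Aim 1 has no rule for repeat entries, and Debrief item 4 lets the second entry repeat the topic just studied

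*Combined protocol and SAP*

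**What the plan says.** The Overview under Research Design and Methods gives the size in people: "We aim to enroll a maximum of 320 subjects with cirrhosis". It then describes each arm's 160 as responses and ends recruitment on completed sessions, 40 per subgroup: "Enrollment will conclude once 160 subject-experiments have been completed for each study arm". The same section lets a participant be randomised again and take part a second time.

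Two places say where a returning participant goes. The Overview gives an example: "if they were randomized into subgroup 1A.1 in the first round, they would be randomized into 1A.2 or 1B.4 for their second round". Debrief item 4 states a rule: "If participants elect to re-enroll, they will be randomized into a different subgroup of the same study arm".

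On analysis, the Post-Evaluation section says: "The change in score between pre-and-post-evaluations for each participant will inform the results of aims 1 and 2". The whole Aim 1 plan is one line: "Aim 1: Matched pair Wilcoxon comparing pre-test and post-test scores in the whole study population". The Pre-Evaluation section gives the purpose of the first quiz: "to determine each participants' baseline level of content knowledge". Nothing in the Statistical Analysis section mentions second entries.

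**The concern.** There are two linked gaps.

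**Unit of analysis.** The pairing in Aim 1 links the pre and post scores of one session. It does nothing about two sessions by the same person. A change score per participant is undefined for someone who has two. If both are entered as separate observations and a person's two changes are positively correlated, the standard error is too small and so is the p-value.

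**Baseline of the second entry.** Under the Debrief wording, someone who has just read the general text (1A.1) can be sent to the general video (1B.3). The second Pre-Evaluation then follows study of the same content. The questions are probably the same too, although the protocol does not say that the two formats share a question set. That score is not a baseline, and the gain from it is compressed. Such records cannot be repaired after collection, only excluded.

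The two effects pull in opposite directions for Aim 1: the first overstates the evidence and the second understates the gain.

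**Working it through.** **1. The plan's own count.** 8 subgroups × 40 = 320, and 2 arms × 160 = 320. The figure reproduces as a count of records. The protocol states no significance level, power, effect size or standard deviation, so there is no power calculation to reproduce.

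**2. People behind the 320 records.** Let f be the share of people who enter twice (not in the protocol; assumed). People = 320/(1+f), and second entries n2 = 320f/(1+f).

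**3. Effect on the Aim 1 error rate.** Let rho be the correlation between one person's two change scores (assumed 0.2-0.5). Each person with two records adds 2·rho to the variance of the sum, in units of the variance of one change. Hence:

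- design effect DE = 1 + (2·n2/320)·rho
- actual alpha = 2·(1 − Φ(1.96/√DE)), with two-sided 5% assumed
- effective N = 320/DE

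Example, f = 0.50 and rho = 0.5: n2 = 160/1.5 = 107; DE = 1 + 0.667 × 0.5 = 1.33; alpha = 9.0%; effective N = 240.

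In each pair below, the first value is for rho 0.2 and the second for rho 0.5.

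| f | People | n2 | DE | Effective N | Alpha, formula | Alpha, simulated |
|---|---|---|---|---|---|---|
| 0.10 | 291 | 29 | 1.04 / 1.09 | 309 / 293 | 5.4% / 6.1% | 4.9% / 6.0% |
| 0.25 | 256 | 64 | 1.08 / 1.20 | 296 / 267 | 5.9% / 7.4% | 6.3% / 6.8% |
| 0.50 | 213 | 107 | 1.13 / 1.33 | 282 / 240 | 6.6% / 9.0% | 6.3% / 8.5% |
| 1.00 | 160 | 160 | 1.20 / 1.50 | 267 / 213 | 7.4% / 11.0% | 7.5% / 10.7% |

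The last column simulates the signed-rank test on all records (normal changes, 8,000 runs per cell, Monte Carlo standard error about 0.3 points). At rho = 0 the simulated rate is 4.9-5.2%. The signed-rank test on each person's average change gives 4.6-5.3%, and on first entries only 4.8-5.5%.

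The quizzes have only 5-6 questions, so the check was repeated with changes rounded to integers, which creates ties. At rho 0.5 the all-records rate was about 7-7.6% at f = 0.25 and 10.5-11.1% at f = 1. Averaging within person brought it back to about 5%.

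**4. Where a returning participant can go.**

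| First entry | Overview example, extended to each start | Debrief item 4 | Same topic under item 4 |
|---|---|---|---|
| 1A.1 | 1A.2, 1B.4 | 1A.2, 1B.3, 1B.4 | 1B.3 |
| 1A.2 | 1A.1, 1B.3 | 1A.1, 1B.3, 1B.4 | 1B.4 |
| 1B.3 | 1A.2, 1B.4 | 1A.1, 1A.2, 1B.4 | 1A.1 |
| 1B.4 | 1A.1, 1B.3 | 1A.1, 1A.2, 1B.3 | 1A.2 |

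None of two destinations repeats the topic under the Overview example; one of three does under Debrief item 4. Arm 2 has the same structure.

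**5. Dilution of the Aim 1 gain.** With equal allocation among three destinations (assumed), same-topic repeats = n2/3. The loss in mean gain is their share of the 320 records multiplied by the fraction of the usual gain that they lose.

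| f | Same-topic records | Share | Loss if half the usual gain | Loss if no gain |
|---|---|---|---|---|
| 0.10 | 10 | 3.0% | 1.5% | 3.0% |
| 0.25 | 21 | 6.7% | 3.3% | 6.7% |
| 0.50 | 36 | 11.1% | 5.6% | 11.1% |
| 1.00 | 53 | 16.7% | 8.3% | 16.7% |

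**6. Aim 2.** The plan names a matched-pair test here too, so an unpaired rank-sum on all records was used as a substitute (f 0.10-1, rho 0.2-0.5). The rejection rate was 4.3-5.2% when the topic always changes and 3.4-5.0% when any other subgroup is allowed. This is not a false-positive problem for Aim 2.

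**The case against.** **The Overview governs.** Its example leaves out the same-topic subgroup, and the Debrief sentence can be read as a shorter summary of the same rule, offered so that people can learn more. On that reading no same-topic repeats occur and every figure in step 5 is zero. The reading is fair, and those figures are conditional on the Debrief wording being the one applied. But someone building REDCap from the Debrief section alone would program three destinations, so the two places need to agree.

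**The Aim 1 answer is unlikely to change.** In the worst case the corrected threshold on the naive z is 1.96 × √1.5 = 2.40. On 320 records that is a mean gain of 2.40/√320 = 0.134 SD, against 1.96/√320 = 0.110 SD uncorrected. At f = 0.25 and rho 0.5 the window is 0.110 to 0.120 SD. Participants answer identical questions before and after open-ended study, so a gain in so narrow a band would be unlucky. This stands, and it limits the severity.

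**The size is assumed.** Uptake, rho and the 5% level are not in the protocol, and changes on two different short quizzes may correlate weakly. At rho 0.1 the formula gives only 5.2%, 5.5%, 5.8% and 6.2% at the four uptake levels. This also stands. It does not supply the missing rule.

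**The main question is untouched.** The Background and Significance section presents text against video as the essential purpose, and no inflation was found there. Agreed, subject to the substitute test.

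**Conclusion.** The concern holds. The protocol allows two records per person, gives Aim 1 no rule for them, and describes re-enrolment in two ways that admit different destinations. Treating all records as independent would put the true level of a nominal 5% Aim 1 test between about 5.4% (10% uptake, rho 0.2) and 11.0% (100% uptake, rho 0.5, an extreme bound), with effective N from 309 down to 213. With no within-person correlation there is no inflation. If the Debrief wording is applied with equal allocation, 3% to 17% of records would have a spoiled baseline, and the mean gain would fall by 1.5% to 16.7% depending on uptake and on how much gain those repeats lose.

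This should be settled before analysis, because a choice between all records and first entries made after seeing results would be open to question. It does not threaten the study: the effect is slight at low uptake, and a clear Aim 1 gain would survive correction.

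**What to change.** 1. **One re-enrolment rule.** Reword Debrief item 4 to match the Overview example: at most one second round, always on the other topic. Program the REDCap branch to enforce it.
2. **Aim 1 unit.** State that the participant is the unit of inference. Average each person's changes, as percent correct because the quizzes have 5-6 questions, before the signed-rank test; or use a signed-rank test adjusted for clustering by person. Give first entries only as a sensitivity analysis. If repeat records enter Aim 2, account for participant and round there.
3. **Sample size wording.** Describe the size as 320 subject-experiments from between 160 and 320 people, and report the number of unique participants.

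The cost is a few sentences and one branching rule. No more patients are needed, and Aim 1 p-values become slightly larger. The Privacy and Confidentiality section describes study ID numbers and a screening log that maps them to email addresses, so a person's two entries should be linkable; the plan should confirm this.
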